Adverse Events will be assessed and monitored according to the established RII's SOPs and the IRB of record's policies and procedures. Reporting Adverse Events, Unanticipated Problems Involving Risks to Subjects or Others (UPIRSOs), and Deviations to the Office of the IRB. All adverse events, unanticipated problems involving risk to subjects or others, and deviations will be reported to the Institutional Review Board (IRB) in accordance with current IRB policy. UPIRSOs and recurrent non-compliance with study procedures will be reported promptly to the IRB. All adverse events that do not meet the UPIRSO criteria and deviations that are not non-compliance will be summarized at Continuing Review per the IRB of record's policy.

Research Monitor.

The study Research Monitor, [name], BPharm, will oversee the safety of the research and report observations/findings to the IRB or a designated institutional official. The IRB assigned Research Monitor's duties include: Act as an advocate regarding complaints or concerns from subjects; verify the IRB approved safety monitoring plan is being followed; verify that UPIRSO determinations are made in a timely fashion; and concurrently review UPIRSO reports submitted by PI to the IRB. In addition, the Research Monitor will review all unanticipated problems involving risks to subjects or others associated with the protocol and provide an independent report of the event to the IRB. The Research Monitor may discuss the research protocol with the investigators, interview subjects, and consult with others outside of the study about the research; shall have authority to stop a research protocol in progress, remove individual subjects from a research protocol, and take whatever steps are necessary to protect the safety and well-being of subjects until the IRB can assess the monitor's report; and shall have the responsibility to promptly report their observations and findings to the IRB or other designated official.

Data Analysis

Neuroimaging Data Analysis Plan: Structural MRI: The T1- and T2-weighted images will be pre-processed using FSL's Brain Extraction Tool (Smith, 2002), then segmented into three tissue classes: gray, white and ventricular components, using the FMRIB's Automated Segmentation Tool (FAST; Zhang et al., 2001). Acquisition of both the T1- and T2-weighted images allow more accurate tissue segmentation and TMS treatment planning; the gray-matter surface normal will be used for treatment planning. Images will be spatially normalized to Montreal Neurological Institute space for group-wise analyses. The DTI data will be pre-processed using FSL's diffusion toolbox.

BOLD fMRI for motor threshold assessment. Each subject's BOLD fMRI will be analyzed using FSL's FEAT program to determine his/her primary motor cortex targets for motor threshold assessment. This information will be used to determine the TMS intensity needed for each subject's iTMS treatment plan and it will also inform the train durations of each treatment session so that the intensity of these pulses falls within the published safety limits of TMS delivered at 10 Hz.

Intrinsic Connectivity by BOLD fMRI. Data will be analyzed using FSL's FEAT program. Head movements are corrected by affine registration using a 2-pass procedure. BOLD data will be normalized to MNI space single-subject template using the "unified segmentation" approach, followed by a 5-mm full width at half maximum Gaussian smoothing. Spurious correlations with nuisance variables are removed using a recently validated framework. Data are band-pass filtered preserving frequencies between 0.01 and 0.08 Hz. The time course of each seed region's BOLD signal will be extracted as the first eigenvariate of activity in all gray-matter voxels located within the respective cluster. To quantify resting-state functional connectivity linear (Pearson) correlation coefficients between the time series of the seeds (targeted DLPFC nodes of each subject's DLPFC-limbic and DLPFC-motor networks) and any other gray matter voxel will be computed. Voxel-wise correlation coefficients will be transformed into Fisher's Z-scores (with non-sphericity correction). These images will be used for iTMS treatment planning. The resting-state fMRI scan will also be used to assess, network-specific functional connectivity differences between each subject's pre-treatment and post-treatment scans.

Clinical Outcomes Data Analysis plan. All pre-treatment and post-treatment MRIs will be acquired and analyzed at the RII, however, all of the statistical analysis of the symptom scores for this project will be done upon completion of recruitment and termination group blinding. The primary efficacy outcome measure will be the PHQ-9 for MDD symptoms assessed pre-treatment, weekly during treatment, post-treatment, and 1/3-months following the completion of treatment and the MADRS for the diagnosis of MDD assessed pre-treatment, post-treatment, and 1/3-months following the completion of treatment. The primary analysis will use

mixed effects regression models. Secondary analysis will focus on changes in MDD symptoms clusters, effects of the intervention in mood symptoms, functioning and cognitive outcomes. Types and rates of adverse events will be summarized and compared across the study groups. The durability of benefit and the clinical significance of PHQ-9 changes will be explored. Non-compliance to protocol as defined as missing three consecutive irTMS sessions or receiving less than 10 irTMS sessions during treatment at their treatment clinic will be assessed for and evaluated in data analysis.

Discontinuation of Subjects. Subjects may be discontinued from study treatment and assessments at any time. Specific reasons for discontinuing a subject from this study are: 1) Voluntary discontinuation by the subject, who is at any time free to discontinue his/her participation in the study without prejudice to further treatment; 2) Clinical deterioration: The following are objective criteria for clinical deterioration, a 25% increase in the PHQ-9 at any time during the study and/or the onset of active suicidality as assessed by the study clinicians requiring treatment outside of the study protocol; 3) Evidence of intolerable adverse reaction, or unable to tolerate irTMS or MRI; 4) Non-compliance to protocol by missing three consecutive irTMS sessions or as judged by the investigator; 5) Safety reasons as judged by the investigator.

Item 7 Risks Section:

Complete the following table to describe the risks of all **research procedures** listed in Step 2, Institutional Form (items 28-34). *Do not list risks of Routine care procedures here.*

N/A, Risks are described in the informed consent document – do not complete this table.

Research procedures

example:

- History and physical
- Questionnaire
- Laboratory tests

Add or delete rows as needed

Risks

List the reasonably expected risks under the following categories as appropriate:

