
Item 4 Purpose and rationale Insert purpose, objectives and research questions/hypotheses here. If you cut and paste from another document, make sure the excerpted material answers the question
	
We propose a randomized, double-blind, trial of iTMS to the left DLPFC for patients with MDD receiving treatment at the treatment clinic. In addition to treatment as usual, subjects will be randomized to receive iTMS in one of three treatment arms: Arm 1 delivers active iTMS to the left DLPFC using the SOC aiming strategy. Arm 2 delivers active iTMS to the left anterior DLPFC using connectivity-based, image-guided aiming. Arm 3 delivers active iTMS to the left posterior DLPFC using connectivity-based, image-guided aiming. In all three arms, repetitive TMS (rTMS) is administered in an image-guided, robotic manner to ensure therapist blinding and equivalent subject experiences across arms. In all three arms, the following stimulation protocol will be used: 10 Hz iTMS delivered in 4 sec trains with 26 sec inter-train intervals, 37.5 minutes/session (i.e. 3,000 pulses/session), 5 sessions/week, for at least 4 weeks. Neuroimaging will be used both for treatment planning and to characterize any TMS-induced network plasticity using resting-state fMRIs (rs-fMRIs) at week 4 of each treatment arm. Clinical assessments will be administered weekly throughout the TMS Treatment Phase. rs-fMRIs will be used both for treatment planning (baseline imaging), which guides the individualized positioning of the TMS coil, and to characterize iTMS-induced network connectivity (week 4). Clinical assessments using relevant clinician rated and self-report scales will be done weekly at the subject's treatment clinic. Other psychological tests will be performed at baseline, and week 4 when participants go to the RII for neuroimaging. Also, 1 and 3-month post-treatment clinical follow-ups will be conducted either in-person or over the phone to evaluate maintenance of clinical outcomes. If a subject's third-party insurance provider approves TMS treatment for more than 4 weeks, clinical assessments should continue on a weekly schedule and the 1 and 3-month post-treatment clinical follow-ups will be conducted (at their respective intervals) following that subject's last TMS treatment session.
 
Aim 1. In persons with drug-resistant MDD compare the treatment efficacy of connectivity-image-guided rTMS targeting anterior DLPFC (Arm 1), posterior (Arm 2) DLPFC and the FDA-approved SOC rTMS targeting protocol (Arm 3). In all 3 arms, at least 4 weeks (5 days/week) of the FDA-approved SOC stimulation protocol (10 Hz x 37.5 minutes) will be used.
 
 • Hypothesis 1a. Connectivity-based iTMS to the anterior left DLPFC will be superior to connectivity-based rTMS to the posterior left DLPFC and standard of care iTMS to the left DLPFC in relieving MDD symptoms. • Hypothesis 1b. Connectivity-based rTMS to the posterior left DLPFC will be superior to the standard of care iTMS to the left DLPFC in relieving MDD symptoms. 
Aim 2. Test for rTMS-induced changes in network functionality (plasticity) using rs-fMRI.
 
 • Hypothesis 2a. Intrinsic connectivity will be attenuated by active iTMS in networks connected to the respective treatment sites, as tested by correlation with the number of sessions received at the time of scanning and by pre-treatment-to-post-treatment contrast. • Hypothesis 2b. Treatment-induced decreases in connectivity will correlate with symptom improvement within and across treatment arms.

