Step-by-Step Methods: We propose to study 150 subjects (i.e. 50 per arm) who meet criteria for 1) MDD as determined by the MINI and 2) treatment resistance as determined by the MADRS) and the outlined study inclusion criteria. We anticipate recruiting and screening approximately 300 male and female subjects, in order to meet the target enrollment goals. To account for subject dropouts and retain a sample of 150 subjects completing the double-blind treatment phase (50 per treatment group), 198 eligible subjects (66 in each group) meeting MDD criteria, as determined by the MADRS, and the study inclusion criteria outlined above, will be randomized for the study. Subjects will be recruited at their treatment clinic from the institution's MDD out-patient program by the Site-Principal Investigator's team. Subjects will be screened for pregnancy and for metal objects in the body before enrolling in the study. The RII Principal Investigator's (PI) team will randomly assign subjects to one of the three treatment arms as part of the generation of neuroimaging-based treatment plans. In addition to rTMS treatments, all subjects will also complete treatment as usual at their treatment clinic, including regular medication management encounters with their attending psychiatrist and therapy sessions as part of their MDD treatment. An effort will be made to limit the disruptions in subjects' treatment by working research assessments and rTMS around their expected programming. Once enrolled, all subjects (N=198, 66 per treatment arm, expecting to retain 50 completers) will be imaged at the RII using a research-dedicated 3T Siemens TIM/Trio MRI scanner (Siemens, Erlangen, Germany) with an eight-channel phased array coil. Structural imaging will be obtained only once, upon enrollment. Structural images will be used for rTMS treatment planning (described below) and for spatial normalization to a standard anatomical template. Functional images will be obtained two times (i.e. pre-treatment and post-treatment-week 4) across the course of the study and used to detect symptom-specific network abnormalities and treatment-induced plasticity. Each subject will wear foam earplugs during each image acquisition session and each rTMS treatment session to protect subjects from the high decibel level produced by the MRI gradient and rTMS coil. See also Table of Study Procedures below.

Recruitment

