angle = 9°, slice thickness = 1.0 mm, in-plane resolution = 1.0 x 1.0 mm² acquiring 256 volumes. T2-weighted images will be obtained with and without fat suppression (turbo spin echo, 34 axial slices, matrix size = 640 x 640, voxel size = 0.4 x 0.4 x 5.2 mm³, flip angle = 120°, TR/TE = 14000/93 ms, turbo factor 18). Total structural MRI scan time is approximately 20 minutes. To ensure accurate irTMS treatment planning, we will also acquire diffusion tensor images (DTI). DTI will be obtained from the diffusion-weighted images using a single-shot echo-planar gradient-recalled echo, T2-weighted, sequence to acquire diffusion-weighted data with the spatial resolution of 2.0 x 2.0 x 2.0 mm and TE/TR = 85/9300. The diffusion-weighted scans will have 64 different non-collinear diffusion sensitization directions, consisting of diffusion-weighted images at b = 700 mm²/s and one non-diffusion weighted image at b = 0 mm²/s. The total DTI sequence acquisition time will be 20 min.

BOLD fMRI for motor threshold assessment. Functional images will also be used to identify each subject's primary motor cortex for motor threshold assessment. BOLD fMRI will be acquired in a block design paradigm utilizing gradient echo planar images with the following parameters: TR = 2.5 s, TE = 30 ms, a flip angle of 90°, and slice thickness = 4.0 mm. Thirty-six continuous slices will be acquired, with an in-plane spatial resolution of 1.7 x 1.7 mm². During the BOLD fMRI scan, participants will perform abduction and adduction of the right index finger (in a block design); this has been shown to maximally activate the first dorsal interosseous muscle area of the hand's motor cortex. The task and rest periods are 50 seconds long and are interleaved during the 6 minutes of data acquisition. During the rest period, the participants will be instructed to remain motionless, to keep their eyes open, and to perform no behavioral task.

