Intrinsic Connectivity by Blood-Oxygen-Level-Dependent (BOLD) fMRI for computing treatment plans. Intrinsic connectivity networks will be measured using blood oxygen dependent (BOLD) fMRI. BOLD fMRI is the most robust and widely used pulse sequence for intrinsic connectivity modeling. BOLD images will be used for computing treatment plans and for testing for intrinsic connectivity changes by symptom score and with treatment. BOLD data will be acquired as 360 whole-brain volumes acquired with a TR = 2500 ms, TE = 30 ms, tip angle = 90°, 128 x 128 voxels, 1.7 mm x 1.7 mm, and 36 slices (4.0 mm thickness). This sequence requires ~ 15 minutes. Resting-state BOLD (15-min acquisition) will be used to map (per-subject) the voxel-wise intrinsic connectivity of DLPFC with the anterior cingulate cortex (ACC) and Precuneus; this will guide aiming parameters.

Motor Threshold Assessment. After the baseline MRI session, each subject will undergo a brief motor threshold assessment by single pulse TMS to their primary motor cortex hand region which elicits a contraction of the targeted hand muscle. The motor threshold assessment begins by locating the hand region and applying single pulses of TMS—with at least 5 seconds between successive pulses—at increasing levels of TMS intensity. We continue to ramp up the TMS intensity with each TMS pulse until we observe a contraction of the targeted hand muscle in 5 out of 10 pulses at a given TMS intensity. This TMS intensity will then be recorded as that subject's resting motor threshold.

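### In the two connectivity-guided arms, Hypothesis 2a reuses the targeting scan as its baseline, so regression to the mean can bias the pre/post contrast at connections used for target selection

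*Combined protocol and SAP*

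**What the plan says.** All places are in the combined protocol and SAP.

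- **Test (Item 4, Aim 2, Hypothesis 2a).** Two analyses are named: "as tested by correlation with the number of sessions received at the time of scanning and by pre-treatment-to-post-treatment contrast". Hypothesis 2b then correlates the decreases with symptom improvement, within and across arms. Neither names a between-arm comparison of connectivity change.
- **Baseline scan used for targeting.** Item 4: "rs-fMRIs will be used both for treatment planning (baseline imaging), which guides the individualized positioning of the TMS coil". Item 6, on intrinsic connectivity for treatment plans, says the resting-state run will "map (per-subject) the voxel-wise intrinsic connectivity of DLPFC with the anterior cingulate cortex (ACC) and Precuneus; this will guide aiming parameters".
- **Same scan used for testing.** The same part of Item 6: "BOLD images will be used for computing treatment plans and for testing for intrinsic connectivity changes by symptom score and with treatment". The Neuroimaging Data Analysis Plan correlates "the seeds (targeted DLPFC nodes of each subject's DLPFC-limbic and DLPFC-motor networks) and any other gray matter voxel will be computed", and adds: "The resting-state fMRI scan will also be used to assess, network-specific functional connectivity differences between each subject's pre-treatment and post-treatment scans".
- **Number of scans (Item 6, Step-by-Step Methods).** "Functional images will be obtained two times (i.e. pre-treatment and post-treatment-week 4) across the course of the study". No split-half, second baseline run or other localiser is described.
- **Arms concerned (Item 6, irTMS Treatment Planning).** The anterior and posterior targets are connectivity-based. The standard-of-care target follows a 5-cm rule.

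**The concern.** A site picked because its measured coupling looks extreme is picked partly for its measurement error. That error is not repeated at week 4, so the measured value moves back toward the average even if treatment does nothing. Here the picked site is the seed, and the value that picked it is the pre-treatment value.

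Hypothesis 2a is the plan's test of treatment-induced plasticity. ACC is an aiming region and also part of the network that Item 3 links to anterior DLPFC, so the exposed connection is central in that arm. A within-arm fall there could be partly or wholly a selection effect. Under the opposite selection rule, a real fall could be missed.

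**Working it through.** **Inputs from the plan.** 50 completers per arm; one pre and one week-4 functional scan; aiming by DLPFC coupling with ACC and Precuneus. The plan gives no sample-size figure for Hypothesis 2a, so there is none to reproduce.

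**Assumptions, not in the documents.** The target is the best of k = 2, 3 or 5 candidate sites on measured coupling. Scan-rescan reliability ρ is 0.6, 0.8 or 0.9. There is no treatment effect, and the test is a paired t-test at one-sided 2.5%.

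**Model.** pre = T + e1 and post = T + e2, with var(T) = ρ and var(e) = 1 − ρ, so the total SD is 1. Then:

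- expected spurious drop = (1 − ρ) × m, where m is the expected maximum of k standard normals (0.564, 0.846, 1.163);
- standard error = √(2(1 − ρ)/50);
- false attenuation ≈ P(Z > 1.96 − drop/SE).

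Example, ρ = 0.8 and k = 2: drop = 0.2 × 0.564 = 0.113; SE = √(0.4/50) = 0.089; ratio 1.26; P(Z > 0.70) = 24%.

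**1. Positive-coupling rule, independent site noise, tested connection = selection metric (worst case).** Drop in SD units, then simulated false attenuation:

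| ρ | SE | k = 2 | k = 3 | k = 5 |
|---|---|---|---|---|
| 0.9 | 0.063 | 0.056; 14% | 0.085; 26% | 0.116; 45% |
| 0.8 | 0.089 | 0.113; 24% | 0.169; 48% | 0.233; 74% |
| 0.6 | 0.126 | 0.226; 45% | 0.339; 79% | 0.465; 97% |

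A fixed site gives 2.3–2.6%.

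**2. Noise shared between candidate sites.** Shared noise cannot drive selection. With noise correlation r, the drop becomes (1 − ρ)(1 − r)·m / √(ρ + (1 − ρ)(1 − r)).

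- r = 0.5: at ρ = 0.9, k = 2 the drop is 0.029 and the rate 7%. At ρ = 0.6, k = 5 the drop is 0.260 and the rate 52–54% across simulation runs.
- r = 0.8: 3–14% over the same grid.

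**3. Looser links to selection.**

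- Measured connectivity correlates 0.5 with the targeting score: 7–44%. At 0.25: 4–14%.
- The tested connection's noise correlates 0.3 with the selection noise: 5–19%. At 0.1: 3–6%.

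**4. Negative-coupling rule.** Signed false decreases are 0–0.3%. Power for a true 0.2 SD decrease at ρ = 0.8 falls from 59% to 16%, 5% and 1% for k = 2, 3 and 5. For k = 2: (0.2 − 0.113)/0.089 = 0.97, and P(Z > 0.99) = 16%. If attenuation means shrinkage toward zero, false shrinkage is 12–96% when typical coupling is 1 SD below zero, and 3–68% when it is zero.

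**5. Session-count correlation.** If both scans are pooled (baseline = 0 sessions; attendance assumed Binomial(20, 0.93)), the false-positive rate is 14% (k = 2, ρ = 0.9), 26% (k = 3, 0.9), 47% (k = 3, 0.8) and 97% (k = 5, 0.6). That is the pre/post result to within 1 point. A week-4-only correlation does not use the baseline value and escapes this bias.

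**6. Between-arm contrasts.**

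- Guided seed against the 5-cm seed: two-sided type I error 9–75%, because only one side was selected.
- Both arms at a seed computed by the same rule: 4.9–5.3%.
- Power of the same-seed contrast for 0.3 SD at ρ = 0.8: SE = 0.632 × √(2/50) = 0.126; 0.3/0.126 = 2.37; P(Z > −0.41) = 66% (simulated 66–68%). An unbiased paired test has 91%.

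**The case against.** The strongest reply is that the plan states no selection rule. Number of candidates, sign, and weight given to anatomy or DTI are all assumed here, and signed false attenuation runs from near 0% to 97% depending on them. This stands: the documents show that bias can arise, not that it will. A reader might infer that any attenuation found in the guided arms is an artefact, or that 97% is the expected error rate. Neither is supported.

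The mitigating features are real. Candidate sites lie within one region, data are smoothed at 5 mm, and the seed is a cluster eigenvariate, so site noise is probably partly shared. Hypothesis 2a also concerns whole networks, and for most connections the weak-link rates are the closer case. The posterior arm is least certain: Item 3 ties posterior DLPFC to mid-cingulate and premotor cortex, whereas aiming uses ACC and Precuneus.

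Hypothesis 2a is not a between-arm hypothesis, and all arms are active. A reader might conclude that a between-arm test must replace the planned contrast. That goes too far: it asks a different question and costs power, and the planned contrast is sound for the 5-cm arm's own site.

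Finally, the week-4 session-count test avoids this bias. It is still weak support, because with a single post scan the count varies mainly through missed sessions, which are not randomised.

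**Conclusion.** The concern holds as a conditional bias. Choosing the seed and measuring its baseline on the same scan, with no independent localiser, is in the plan. It is more than missing detail, because following the plan as written can give a misleading result at ACC, Precuneus or noise-sharing connections in the guided arms.

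Direction depends on the unstated sign of the rule and on whether attenuation is signed or absolute. Size depends on the assumed k, reliability and noise sharing: severe in the worst case, slight where noise is largely shared or the connection is weakly linked to selection.

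A reader might extend this to the trial's efficacy conclusions. The documents do not support that, since PHQ-9 and MADRS play no part in choosing the seed. The point should be fixed; confidence in its size is medium.

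**What to change.** 1. State the target-selection rule and its sign, and say whether attenuated means signed or absolute change.
2. For analysis only, compute the anterior and posterior targets by that rule from every subject's baseline scan, in all three arms and blind to arm.
3. Add to Hypothesis 2a a randomised arm-by-time contrast at the same computed seed: anterior against posterior arm at the anterior seed, and the mirror test at the posterior seed. Subjects in the 5-cm arm may also serve as comparators at that computed seed. Do not compare a guided seed with the 5-cm seed.
4. Base claims of treatment-induced change at selection-linked connections on that contrast. Report within-arm change there with a selection-bias caveat.
5. Keep the planned within-arm contrast for connections not linked to selection and for the 5-cm arm. Label the session-count correlation exploratory.

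**Cost.** Wording and offline computation on scans already planned; treated sites, scans and visits do not change. The added contrast tests site-specific change only, so attenuation common to both sites cancels. Power for a 0.3 SD decrease is about 67% against 91% at reliability 0.8 (39–43% against 64–65% at 0.6; 92% against over 99% at 0.9). If half the effect spreads to the other site, it is about 22% at 0.8. Adding the 5-cm subjects as comparators would help if their stimulation leaves that seed unchanged: SE = 0.632 × √(1/50 + 1/100) = 0.110, 0.3/0.110 = 2.74, power about 78%. Unequal loss of post scans between arms could still bias the contrast.
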